#### **7.8.4. Secondary Objective #2**

The second secondary objective aims to estimate the probability of post implant lead failure through 6 months for each individual failure type (e.g. lead dislodgement, infection, device capturing issue).

##### **Analysis Dataset:**

To proactively address FDA reviewer's potential questions at the time of PMA-s submission, two approaches will be considered: (a) standard frequentist approach and (b) Bayesian approach borrowing information from historical datasets. Per FDA requirement, the study reports will provide standard frequentist estimates as primary results. The analysis dataset will consist of all subjects successfully implanted with the Attain Stability Quad MRI SureScan LV Lead (Model 4798) and who completed at least 6-month follow-up or experienced lead failure prior to 6-months (i.e. Analysis set #3 per section 7.1.3.). For the Bayesian approach, analysis will be performed using data from the first 360 subjects successfully implanted with the Attain Stability Quad MRI SureScan LV Lead (Model 4798) and who completed the 6-month follow-up. In addition, the Bayesian approach will use historical datasets from the Attain Stability and Attain Performa clinical studies, described in more detail below.

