#### **Analysis Set #3:**

All subjects who are successfully implanted with a Model 4798 lead and who completed the 6-month post implant follow-up visit or experienced lead failure prior to 6-months.

If a subject experienced multiple Model 4798 lead implant procedures (e.g. a second lead was implanted due to a system modification of the initialed implanted lead), only first experience will be included for the analysis. Multiple lead attempts during this same procedure will not be counted as multiple procedures.

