###### **Bayesian Approach**

The Bayesian analysis will be conducted as a virtual adaptive study. The interim look dataset will be constructed as it would have been available after the 360th patient was enrolled, and the additional enrollment will be computed. The final analysis will be conducted using only the data from the interim and additional enrollment, along with the historical prior data, to simulate the results of an adaptive study.

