### Comparison

Let  $y$  and  $y_0$  be the number of events that occur for the current data and historical data respectively and let  $n$  and  $n_0$  be the total number of subjects for the current and historical studies that reach the 6 month time point or had an event. A discount function is used to adjust the strength of the prior according to the agreement between current and historical data.

Suppose we develop the posterior distribution of  $\tilde{\theta}$  and  $\theta_0$  for the current data and historical data, respectively, both with minimally informative priors. Calculate  $\theta$  as:

$$\tilde{\theta} \sim \text{beta}(y + 1, n - y + 1) \quad (1)$$

$$\theta_0 \sim \text{beta}(y_0 + 1, n_0 - y_0 + 1) \quad (2)$$

We can stochastically compare the distribution of  $\tilde{\theta}$  to  $\theta_0$  as follows:

$$p = P(\tilde{\theta} \leq \theta_0 | y, n, y_0, n_0) \quad (3)$$

Equation (3) can be calculated by drawing  $m$  samples of  $\tilde{\theta}$  and  $\theta_0$  from (1) and (2) (i.e.  $\tilde{\theta}^1, \tilde{\theta}^2 \dots \tilde{\theta}^m$  and  $\theta_0^1, \theta_0^2 \dots \theta_0^m$  )

$$p = P(\tilde{\theta} \leq \theta_0) = \frac{1}{m} \sum I\{\tilde{\theta}^i < \theta_0^i\}$$

The resulting p-value is then used to compute the discount function.

[figure not shown]

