### Interim analysis

This analysis will be conducted with data retrospectively analyzed as it would have been available for the first consecutively enrolled 360 subjects. Within this data set, some patients will not have completed the full evaluation period. A longitudinal model will be employed to enable final observations to be imputed for those subjects with incomplete information.

There are 3 types of subjects at a given interim analysis:

1. Subjects that have complete data
2. Subjects that have partial data (censored value at a particular time)
3. Subjects that have no information (subjects that have not been enrolled)

We will construct predictive probabilities for types 2 and 3. The predictive probability model that will be used is a piecewise exponential. This will allow us to impute final outcomes for the subjects who have not had an event and have not completed 6 month follow up.

We assume a gamma distribution prior for each of the exponential segments, which allows us to estimate the hazard rate using closed form conjugacy. Therefore, the posterior is also a gamma distribution.

We partition duration time into 3 intervals across six months (0-2, 2-4, and 4-6 months) and assume the hazard is constant within each interval. The event times are therefore modeled as:

$$T_{\text{event}} \sim \text{PE}(\lambda_1, \lambda_2, \lambda_3)$$

where  $\lambda_1, \lambda_2, \lambda_3$  are the hazards for the three segments.

The purpose of the interim look is to determine the number of additional patients to enroll in order to have a high probability of meeting the required effective sample size of  $n_{\text{effective}} = 400$  (after accounting for attrition). The effective sample size is the sum of enrolled patients and effective historical patients at the final analysis. The interim analysis may result in as few as 363 patients enrolled. This study follows methods from Berry, et.al.

Adaptive Bayesian sample size algorithm:

1. If the predictive probability of  $n_e \geq 400$  is larger than 80% then enrollment will stop.
2. If the predictive probability of  $n_e \geq 400$  is less than 80%, enroll sufficient additional patients to make the probability of  $n_e \geq 400$  at least 80%.

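### Secondary Objective #2: the stated Bayesian data set keeps only 6-month completers, omits early lead failures, and conflicts with the Bayesian method set out later in the same section

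*SAP*

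**What the plan says.** SAP Section 7.8.4 plans two analyses of post-implant lead failure by type: a frequentist one, reported as primary, and a Bayesian one that borrows from two historical studies.

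- **Analysis Dataset, frequentist.** Implanted subjects "who completed at least 6-month follow-up or experienced lead failure prior to 6-months". This is Analysis Set #3 of Section 7.1.3, defined as those "who completed the 6-month post implant follow-up visit or experienced lead failure prior to 6-months".
- **Analysis Dataset, Bayesian.** The "first 360 subjects successfully implanted with the Attain Stability Quad MRI SureScan LV Lead (Model 4798) and who completed the 6-month follow-up". There is no failure clause.
- **Bayesian Approach.** "The interim look dataset will be constructed as it would have been available after" the 360th patient entered. The final analysis uses the interim patients and the additional enrollment.
- **Comparison.** The denominators n and n0 are subjects "that reach the 6 month time point or had an event". The section on combining the data repeats this.
- **Interim analysis.** Data are taken "as it would have been available for the first consecutively enrolled 360 subjects". The text adds: "Within this data set, some patients will not have completed the full evaluation period". Their outcomes are imputed from a piecewise exponential model. The target is an effective sample size of 400.
- **Final Analysis.** Six-month data from the interim patients plus the additional patients that the interim look calls for.

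**The concern.** The Analysis Dataset paragraph is where a programmer looks for the population, and its Bayesian sentence gives a different one from the method text that follows. The endpoint is lead failure. A rule that requires a completed 6-month visit can therefore select on the outcome: a subject whose lead fails and who leaves the study before that visit is in neither numerator nor denominator. Analysis Set #3 names early failures separately from completers, so the SAP itself allows for failures without a completed visit.

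The borrowing is exposed too. The historical weight depends on p, the probability that the current failure rate is no higher than the historical one. Losing current failures raises p, and so can raise the weight given to history. Two analysts working from different paragraphs of Section 7.8.4 could report different subjects, rates and amounts of borrowing.

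**Working it through.** **1. The plan's own figures reproduce.** Section 6 needs 400 subjects at 6 months with 15% attrition: 400 / 0.85 = 470.6, rounded up to 471, as stated. The Interim analysis text gives a minimum of 363 patients: 400 − 37 = 363, where 37 is the maximum historical weight under Methodology. Neither figure is disputed.

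**2. Does the completer sentence fit any stage of the Bayesian analysis?**

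| Feature | Analysis Dataset sentence | Method text in Section 7.8.4 |
|---|---|---|
| Ordering | First 360 implanted and completed | First 360 consecutively enrolled (interim) |
| Early failure without a 6-month visit | Excluded | Counted in n (Comparison) |
| Incomplete follow-up at the virtual cut | Not mentioned | Present and imputed (interim) |
| Patients beyond the first 360 | None | Added at the final analysis |

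It is not the interim set, which is defined by enrollment. It is not the final set, which is larger and counts events. The size confirms the second point: 360 + 37 = 397, which is below 400 even at full borrowing.

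**3. Possible effect on the estimates.** The SAP gives neither the number of failures nor the share of failed subjects who miss the visit, so both are assumed here. The SAP's formulas are:

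- current rate ~ beta(y + 1, n − y + 1); historical rate ~ beta(y0 + 1, n0 − y0 + 1)
- p = P(current rate ≤ historical rate)
- a0 = 1 − exp(−(5p)²) for the Attain Stability history
- posterior: beta(y + a0·y0 + 1, (n − y) + a0(n0 − y0) + 1)

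Take fixation failures, where the history is y0 = 0 of n0 = 37, and hold n at 360.

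- **All 18 failures counted.** p = 0.143; a0 = 1 − exp(−0.511) = 0.40; patients borrowed = 0.40 × 37, about 15. Posterior mean = 19 / (360 + 15 + 2) = 5.0%.
- **Half lost, 9 counted.** p = 0.36; a0 = 0.96; about 36 borrowed. Posterior mean = 10 / (360 + 36 + 2) = 2.5%.

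With fewer failures the rate still falls, but the borrowing hardly moves. With 9 failures all counted, the posterior mean is 2.5% with about 36 borrowed. If 4 of the 9 are lost (5 counted, n = 356), it is 1.5% with 37 borrowed.

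**4. The null case.** If every subject with a failed lead completes the 6-month visit, no failure is lost and the rates do not change on this account.

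**The case against.** The strongest reply is that this is loose wording with little riding on it. The Comparison text, which defines the model's inputs, counts events, so an analyst who follows it keeps the early failures. The frequentist estimate is the primary result, already uses Analysis Set #3, and is untouched. Section 4.2 sets no performance requirement for the secondary objectives. All of this stands and limits the consequence. It does not remove the contradiction.

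A reader might also infer more than the documents support:

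- **That every early failure is lost and every failure-mode rate is biased down.** Only failures whose subject misses the 6-month visit are at risk. Section 7.1.1 follows implanted subjects until closure or exit, and its list of example exit reasons does not name lead failure. Section 7.1.3 foresees subjects who receive a second lead.
- **That the imputation model would have nothing to do.** The interim look is reconstructed at a virtual cut, so a subject who later completed may have had only partial data at that point. The model also predicts for subjects not yet enrolled.
- **That 15% attrition leaves about 306 evaluable subjects (360 × 0.85) in the Bayesian analysis.** The interim algorithm adds patients toward an effective 400 after attrition, so 306 does not describe the final set.
- **That borrowing would always be inflated.** With 12 of 363 failing in one mode, about 31 of 37 patients are already borrowed from the Attain Stability history and about 30 from Attain Performa. At most 6 or 7 more can be added.

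**Conclusion.** The data set sentence is wrong as written. It conflicts with the Comparison, Bayesian Approach, Interim analysis and Final Analysis texts of its own section, and 397 cannot meet the target of 400. That conclusion rests on the text and simple arithmetic alone.

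The size of any bias is unknown. It runs from none, if all failed subjects complete the visit, to a halving of the rate in the 18-failure illustration, which assumes both the failure count and a 50% loss. A marked rise in borrowing needs many failures in one mode. The effect is confined to the supplementary Bayesian estimates; neither the primary frequentist estimate for this objective nor any primary objective depends on it. It is worth correcting before analysis, but it does not threaten the study's conclusions.

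**What to change.** Replace the Bayesian sentence in the Analysis Dataset paragraph of Section 7.8.4 with two definitions:

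> *Interim data set:* the first 360 consecutively enrolled subjects, with data as they stood at the virtual cut and incomplete outcomes imputed. *Final data set:* the interim subjects plus the additional enrollment set by the interim algorithm, limited to those successfully implanted who either reached 6 months or had a lead failure before then.

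The final definition must name the additional enrollees; otherwise it would still be capped at 360 and fall short of 400.

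Also confirm that the historical 0 of 37 was counted under the rule that the Comparison text states for n0 (reached 6 months or had an event). Methodology describes those 37 only as having follow-up data at six months or longer, and the SAP does not show whether early failures were left out.

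The cost is one SAP sentence and one check of an existing count. No new data are needed.

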##### **Analysis Method:**

###### **Standard Frequentist Approach**

For each lead failure mode, the Attain Stability Quad LV lead failure rate will be estimated as the number of subjects with Attain Stability Quad MRI SureScan LV Lead (Model 4798) failure before 6 months (183 days) divided by the total number of subjects successfully implanted with an Attain Stability Quad MRI SureScan LV Lead (Model 4798) successfully implanted and who completed at least the 6-month follow-up or had a lead failure before 6 months post-implant. A 2-sided 95% Confidence Interval will be calculated using the Clopper-Pearson method.

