## 6. Determination of Sample Size

The sample size requirement at 6-months for each of the study objectives is displayed in

Table 1. The first row does not account for attrition, while the second row is inflated by 15% attrition which accounts for 5% pre-procedure and 10% post procedure attritions. The sample size requirement for Secondary Objective #2 was given by the FDA as a requirement for evaluating post implant lead failures. Therefore, the overall sample size for the study is 471.

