#### Analysis Method:

A standard time to first event survival analysis type will be performed to investigate the hypothesis proposed in the primary safety objective. More specifically, the Kaplan-Meier method will be used to estimate the probability of a subject surviving from any Model 4798 lead-related complication as a function of time; the 1-sided 97.5% confidence limit lower bound for the survival probability at 6 months (183 days) will be calculated using the log-log survival function approach (Kalbfleisch and Prentice 2002). For the purposes of this analysis, time 0 is defined as the day a subject undergoes the implant procedure of the Attain Stability Quad MRI SureScan LV Lead (Model 4798), which is independent of success status of this implant procedure. For the survival analysis, an event is defined as an Attain Stability Quad MRI SureScan LV Lead (Model 4798) related complication according to Clinical Events Committee (CEC) adjudication. Event date is the onset date of a subject's first complication that is related to the Attain Stability Quad MRI SureScan LV Lead (Model 4798). The definition of "complication" and "LV lead related" can be found on the study CIP. Subjects who undergo an Attain Stability Quad MRI SureScan LV Lead (Model 4798) implant attempt and do not experience any LV lead related complications will have their time to event censored at their last known time to exposure to the initial Attain Stability Quad MRI SureScan LV Lead (Model 4798). For any lost to follow-up subject, the last contact date will be used as the censor date.

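### The primary failure-mode rate keeps early failures but drops subjects who leave failure-free before 6 months, so rates for modes with events generally run slightly high

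*SAP*

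**What the plan says.** Secondary Objective #2 (SAP 7.8.4) "aims to estimate the probability of post implant lead failure through 6 months for each individual failure type". Two approaches are planned, frequentist and Bayesian. Their standing is fixed in the same section: "Per FDA requirement, the study reports will provide standard frequentist estimates as primary results".

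The frequentist numerator is every subject with a failure of the given mode before day 183. The denominator is limited to successfully implanted subjects "who completed at least the 6-month follow-up or had a lead failure before 6 months post-implant". Analysis Set #3 (7.1.3) carries the same rule: subjects "who completed the 6-month post implant follow-up visit or experienced lead failure prior to 6-months". On the interval: "A 2-sided 95% Confidence Interval will be calculated using the Clopper-Pearson method".

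The SAP handles early exit differently for the primary safety objective. There (7.8.1) "the Kaplan-Meier method will be used to estimate the probability of a subject surviving", with censoring at last exposure to the lead or at last contact. Section 7.1.1 lists the exits to expect, including withdrawal of consent, death and loss to follow-up, and promises a sensitivity analysis for missing data without naming a method.

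**The concern.** The quantity wanted is a probability of failure through 6 months after implant. The planned ratio treats two kinds of early leaver differently. Someone whose lead fails before they leave enters both numerator and denominator. Someone who leaves with a working lead enters neither. The denominator thus loses non-failures but never observed failures, which pushes the ratio up.

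The partial follow-up of the failure-free leavers shows that their leads worked until they left, and this estimate does not use it. Nothing else in 7.8.4 repairs that. The piecewise-exponential model serves only the interim step of the Bayesian approach, which is not the primary result.

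The objective is descriptive, so its point estimates and intervals are all that it delivers. It is also the objective that sets enrolment at 471.

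**Working it through.** **Inputs from the SAP**
- Number needed at 6 months for this objective: 400 (Table 1).
- Attrition (section 6): the enrolment figure is "inflated by 15% attrition which accounts for 5% pre-procedure and 10% post procedure attritions".
- Illustrative rate: 10/401 = 2.49%, the historical non-fixation complications in 7.8.4, all types pooled. The SAP plans no rate per mode, so this is an assumption.

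**The plan's own figure.** 400/(1 − 0.15) = 470.6, rounded up to 471. This reproduces Table 1. It implies 471 × 0.95 ≈ 447 subjects reaching the procedure (taken here as implanted), 471 × 0.10 ≈ 47 later exits, and 471 × 0.85 ≈ 400 completers. As a share of those implanted, exits are 47.1/447.45 = 10.5%.

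**Direction.** Let F be the failure probability by 6 months, S = 1 − F, and G(t) the probability of still being in the study at t, with exit independent of failure. The expected observed failure fraction is Obs = ∫G dF, which is at least G(6)F because G only falls. The planned ratio tends to

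E = Obs / (Obs + G(6)·S) ≥ F.

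Equality needs G(t) = G(6) at every failure time: either no attrition, or every exit comes before the failures begin. The bias is largest when all failures come before any exit.

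**Size at F = 2.494%, exits 10.5%, so G(6) = 0.895**
- All failures at day 0: 0.02494/(0.02494 + 0.895 × 0.97506) = 0.02494/0.89762 = 2.78%, a relative excess of 11.4% (0.28 points).
- Failures spread over the first month: 2.75%, +10.4%.
- Constant hazards for failure and exit: −ln(0.97506) = 0.02525 and −ln(0.895) = 0.11093, so Obs = (0.02525/0.13619) × (1 − 0.87268) = 0.02361. Then E = 0.02361/(0.02361 + 0.87268) = 2.63%, +5.6% (0.14 points).

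Reading the 10% as a share of implanted subjects instead gives 2.63% to 2.76%, or +5.3% to +10.8%.

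**Other rates, exits 10.5%, constant hazard to day 0**
- True 0.5%: reported 0.53% to 0.56%.
- True 5%: reported 5.28% to 5.55%.

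**Simulation** (447 implanted, 10.5% exits, true rate 2.49%, 4,000 runs, no competing events)

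| Failure timing | Planned ratio, mean (SD) | Kaplan-Meier, mean (SD) |
|---|---|---|
| Spread over 6 months | 2.64% (0.80 points) | 2.50% (0.76 points) |
| First month | 2.77% (0.82 points) | 2.51% (0.74 points) |

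Using the partial follow-up removes the bias and gives a somewhat smaller standard deviation.

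**Where the direction can fail**
- *No events in a mode.* The estimate is 0 either way; only the interval changes. The exact upper limit is 0.92% with n = 400 and 0.82% with n = 447.
- *A late-failing mode beside frequent early failures of other modes.* Suppose a true 1% late rate with 5% early failures elsewhere: 0.895 × 0.01/(0.05 + 0.895 × 0.94 + 0.895 × 0.01) = 0.00895/0.90025 = 0.99%, trivially low.
- *Informative exit.* If leavers carry more than about 2.2 times the failure risk of completers and half of their failures go unseen, the bias turns downward. At three times the risk the ratio gives 2.42% against a true 2.49%.

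**The case against.** The strongest case against acting is that little depends on this. Section 4.2 sets no performance requirement for the secondary objectives, the error overstates failure and so works against the device, and the 400 is a count given by the FDA rather than a precision calculation. A shift of 0.14 to 0.28 points is about 0.2 to 0.35 of a standard error (0.14/0.80 to 0.28/0.82), and the exact interval for 10/400 runs from 1.21% to 4.55%. All of this stands and limits the weight of the point. It does not make the ratio an estimate of the stated probability.

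It may also be said that the FDA asked for this analysis. Section 7.8.4 attributes to the FDA only that frequentist estimates be primary. It does not attribute this denominator, and cumulative incidence is also a frequentist estimate. Whether the FDA wanted an evaluable-subject proportion as well cannot be seen from the SAP, which is a reason to keep that proportion in the report.

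Four stronger readings are tempting but not supported:
- A reader might infer that every rate is too high. The exceptions at the end of the working show otherwise.
- A reader might apply the full 15% attrition. Five of those points arise before the procedure, so those subjects were never candidates for this denominator.
- A reader might expect the ratio to disagree with the primary safety Kaplan-Meier result because of this bias. The two would differ anyway: the safety analysis covers any lead-related complication, from the implant attempt, in Analysis Set #1.
- A reader might infer that subjects who miss the 6-month visit but are seen failure-free later are lost. Set #3 alone reads that way, but 7.8.4 asks for at least 6 months of follow-up, which can reasonably include them. At most the wording should be aligned.

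**Conclusion.** The concern holds in limited form. As written, inclusion in the primary per-mode estimate depends on the outcome. When exit is unrelated to failure, the estimate for a mode with events is generally at or above the probability that the objective targets. At the planned post-procedure attrition the relative excess is about 5% to 11%. The upper figure is the extreme in which no one leaves before the last failure.

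The size rests on three assumptions: the SAP's attrition figure, an illustrative 2.5% rate, and independent exit, on which the SAP's own Kaplan-Meier analysis also relies. The calculation treats all exits as censoring. Where an exit is a death and death is taken as a competing event, a failure-free death belongs in the denominator as a non-failure, so dropping it inflates the rate too.

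No success decision is affected. The change is still worth making, because a standard method answers the stated question with less bias and slightly better precision.

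**What to change.** In 7.8.4, Standard Frequentist Approach, make the primary estimate the 183-day cumulative incidence of each failure mode in all successfully implanted subjects:
- Censor at last contact or study exit.
- Treat death and lead removal for another reason as competing events (Aalen-Johansen).
- Report a 95% interval on the complementary log-log scale.
- For modes with no events, where that interval is undefined, report the exact Clopper-Pearson upper limit and name its denominator. The Set #3 count is the cautious choice, because counting every leaver in full assumes that each would have stayed failure-free.

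Keep the present Set #3 proportion with its Clopper-Pearson interval as a supportive result and as evidence that 400 subjects were evaluable. Align the Set #3 wording with the at-least-6-months wording in 7.8.4.

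The cost is a revision of SAP text and one standard procedure. The event and censoring dates are already needed for the primary safety analysis, and enrolment does not change.
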